4 STUDY DESIGN

4.1 OVERALL DESIGN

We will complete a single site, cluster-randomized trial to evaluate the effectiveness of a multi-component implementation strategy (the intervention) to increase use of the HPV vaccine according to CDC guidelines. Randomization will occur after baseline assessment and the unit of randomization is a community-based, primary care pediatric practice. The randomization schema will be generated and implemented by the study statistician. Twenty practices will be randomized into two groups, the 2-year intervention group (n=10) or a wait-list control group (n=10). The intervention includes: 1) an educational video to increase the provider's knowledge about guideline recommendations and patient and practice benefits of vaccination by age 13; 2) audit and feedback of vaccine coverage to increase motivation to engage in practice change; 3) a communication strategy to improve the provider's communication skills and their self-efficacy to address parental hesitation; and 4) practice facilitation to support practice change to develop a sustainable HPV vaccine delivery system. The intervention will be delivered through a series of brief practice visits with the facilitator that occur every 1-4 weeks over 2 years. Vaccine use will be assessed at the practice level using 12-months of routinely collected clinical data to allow for seasonal variation in care delivery patterns. Vaccine use will be assessed at baseline, at 12 and 24 months to assess effectiveness, and at 36 months to assess if change is sustained. Due to the 2020 pandemic and overall concerns for safety, we will use ZOOM video conferencing for research activities, including obtaining measures and implantation of the intervention

The study hypotheses are: 1) *The 2-year intervention will increase the percentage of preteens who receive HPV vaccine before their 13th birthday by at least 13 percentage points, and benefits will be sustained at 36 months.* 2) *The intervention will increase on-time HPV vaccination by increasing providers' capability (communication skills) and their motivation (confidence in their capabilities) to deliver on-time HPV vaccination.*

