6.3 MEASURES TO MINIMIZE BIAS: RANDOMIZATION AND BLINDING

Bias: Although most providers will be from St Louis metropolitan area, they will be drawn from the bi-state area. We will gather information to describe participants and eligible non-participants to assess selection bias and allow others to assess the relevance of our findings to their situation.

Randomization: We will stratify practices into 2-groups by the number of providers. (≤ 4 and ≥ 5) We will randomize within the strata using a block design.

Blinding: It is not possible to blind investigators or practices from group assignment. The RA and the data analyst will be blinded to group assignment and are responsible for assessment of the primary and secondary outcome measures of HPV vaccine use. Blinding is not necessary for baseline measurements as this will occur prior to randomization. Thus, baseline measures may be completed by other members of the study team. In addition, measurement bias will be minimized for the assessment of these outcomes by using a standardized approach for data collection and analysis, as well as quality checks.

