8 STUDY ASSESSMENTS AND PROCEDURES

8.1 ENDPOINT AND OTHER NON-SAFETY ASSESSMENTS

Mixed methods of data collection will be used including audit of the electronic medical record (EMR) to extract routinely collected and previously recorded data, surveys, and field notes. The study team will follow the same measurement procedures for both study groups.

The primary and secondary outcomes (vaccine initiation and completion by age 13, respectively) will be assessed by audit of the EMR, completed by the research assistant (RA) and/or a member of the study team. To assess variation among providers in the same practice, we will sample records from each participating provider. Measurement will be completed over four 12-month time periods (baseline, 12, 24, and 36 months). For each measurement period, the physician's office will provide an electronic list of eligible patients with an office visit with each participating provider. For each practice, a member of the study team will randomly select a sample of 60 records per provider from this list for review by the RA and or other member of the study team. As much as possible the number of records will be balanced across providers. Data abstracted from the record will include date and type of index visit (well child, acute care, and other e.g., immunization), date of birth, date of vaccination for HPV vaccine, Tdap, and MCV, sex, race/ethnicity and insurance status. Records will be de-identified for patient, provider and practice identifiers, and given a unique subject ID number.

Providers: At baseline and at 12- and 24-months, in addition to the EMR audit described above, all participating providers will complete a brief survey to assess their knowledge, attitudes and behaviors regarding HPV vaccination. The baseline survey will also assess demographic and other practices and physician-level factors that may affect intervention success and are needed to describe the study sample. The practice facilitator will keep detailed field notes about practice observations, contextual factors and practice change components, and will monitor the implementation process.

Practices: At baseline, the project coordinator and/or a member of the study team will meet with the practice manager to complete a brief practice survey to describe the practice and current HPV vaccination procedures. HPV vaccination procedures will be reassessed in a similar manner at 12- and 24- months.

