9.2 SAMPLE SIZE DETERMINATIONS

AIM 1: We will use a cluster randomized design. Study outcomes will be measured at the level of the patient using a cross-sectional design. The sample size determination is based on the primary outcome - initiation of HPV vaccination by age 13. Effectiveness is derived from the difference in the proportion of eligible preteens in the intervention and control groups 24 months after the intervention, and long-term maintenance is derived from the difference in these measures 36 months after intervention. In the control group, national data suggest the baseline vaccine initiation proportion should be 0.4. We expect the vaccine initiation proportion in the control group in this age group will not change over time, and intervention group will have a similar baseline initiation rate to the control group, but will increase by at least 0.13 by 24 months. Thus, the hypothesis to test is $H_0: p=0.4$ vs. $H_1: p=0.53$.

Our study has a three level hierarchical structure: children are clustered within providers which are clustered within practices. Thus, there exists correlations for children seen by the same provider, as well as providers working in the same practice. We use random effects to capture the intra-class correlation at the provider and the practice levels. From our preliminary data, the estimate for random effect variance at the practice level is very close to 0, and that at the provider level is 0.75² (corresponding to an ICC of 0.15). This suggests very little heterogeneity at the practice level, but significant heterogeneity at the provider level. Since there is no ready-to-use software for power calculation for clustered trial in the three level hierarchical structure, we conduct the power calculation by simulation.

In the simulation study, we set $\sigma_a^2 = .01$ for the random effect at the practice level and $\sigma_b^2 = .75^2$ for the random effect at the provider level. We choose the value of β so that the proportion of HPV vaccine rate is 0.4 for control and 0.53 for the intervention. We assume there are 4 physicians in each practice, each physician sees 30 children, resulting a total of 120 patients in each practice. The sample size to calculate is the number of practices. The simulation study is carried out in R, using function *glmer()* in the *mle4* package for estimation of the generalized linear mixed effects model (1) below.

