9.4.2 ANALYSIS OF THE PRIMARY ENDPOINT(S)

Data analyses will adhere to the intention-to-treat principle, allowing 12-months grace period to implement practice changes. The primary analysis will compare the overall proportion of eligible preteens who initiated and completed HPV vaccination in the intervention and control practices at 24 months, using Year 2 measurements for vaccine use. Maintenance of change will be assessed using Year 3 measurements. The analytic approach is to use a multi-level random effects logistic model to account for the hierarchical structure: children clustered within providers clustered within practices.

Define by y_{ijk} as the binary variable of HPV vaccine for the k th child of provider j of practice i . There are 3 hierarchical levels: children clustered within providers clustered within practices. We use random effects to capture the intra-class correlation at the provider and the practice levels. We assume a multi-level random effects logistic model (a generalized linear mixed model):

$$\text{logit } P(y_{ijk}=1) = \beta_0 + trt_{ijk}\beta_1 + a_i + b_{ij} \quad (1)$$

[figure not shown]
where trt_{ijk} is the treatment indicator for practice i , and β_1 is the treatment effect. We use random effects a_i and b_{ij} to describe heterogeneity in the practice level and provider level, and assume $a_i \sim N(0, \sigma_a^2)$ and $b_{ij} \sim N(0, \sigma_b^2)$ are independent. The practice level random intercept is used to accommodate extra-variation in outcome measurements due to clustering of providers in a practice, and the provider level random intercept is used to accommodate extra-variation in outcome measurements due to clustering of individual patients within a provider.

As secondary analysis, we can add other covariates in the model, e.g., gender, category of practice (urban vs. rural), vaccine rate at baseline for a provider or practice, etc. Interaction of treatment and these covariates can be included in the model to study the moderating effect of these risk factors. The interaction of random effects (both at the practice and provider levels) and covariates can be added in the model as well.

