9.4.7 SUB-GROUP ANALYSES

We plan two subgroup analyses to explore intervention effectiveness for girls and boys, and for those with Medicaid insurance compared to other health insurance.

As secondary analysis, we can add other covariates in the model used in the primary analysis, e.g., gender, category of practice (urban vs. rural), vaccine rate at baseline for a provider or practice, etc.

Interaction of treatment and these covariates can be included in the model to study the moderating effect of these risk factors. The interaction of random effects (both at the practice and provider levels) and covariates can be added in the model as well.

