9.4.9 EXPLORATORY ANALYSES

As secondary exploratory analyses, we can add other covariates in the model used in the primary analysis, e.g., gender, category of practice (urban vs. rural), vaccine rate at baseline for a provider or practice, etc. Interaction of treatment and these covariates can be included in the model to study the moderating effect of these risk factors. The interaction of random effects (both at the practice and provider levels) and covariates can be added in the model as well.

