10.4 PROTOCOL AMENDMENT HISTORY

Version	Date	Description of Change	Brief Rationale
1.02	12/20/2019	Section 6.3: Blinding not needed for assessment of baseline measures Section 10.1.6: PI will be responsible for safety oversight rather than a safety monitoring committee	Baseline measures are completed prior to randomization. The study is assessed as low risk and a safety monitoring committee is not required by the NIH.
1.03	1/10/2020	Sections 5.5 and 8.1: Removed #30 from the eligible sample list for parent surveys.	To obtain 30 parents/practice, we will need to invite a larger list of eligible parents.
1.04	2/10/2020	Sections 1.1 and 6.11: Added, all providers will receive baseline HPV vaccination rates. Section 6.3: Added stratification to the block design for randomization.	In order to allow all providers to know the results of chart audits. To balance the randomization process for number of providers in the practice.
1.05	3/24/2020	Section 5.5 and 8.1: Clarified who will send an email or text invitation for study participation to parents.	The email or text invitation will come from the study team, providers have the option to send an email or text to the parents.
1.05	3/24/2020	Section 1.2: Study Schema to reflect measurement for 160 preteens per practice	To maintain power and address the variability in the recruited practices (2-8 providers), we increased the sample size of patients.
1.05	3/24/2020	Section: 8.1 and 9.2: Increased sample size to 160 patients/practice.	To maintain power and address the variability in the recruited practices (2-8 providers).
1.06	5/13/2020	Eliminated the parent survey at baseline.	Due to the 2020 outbreak of Covid-19, it is not possible to obtain the necessary information for a parent survey at this time. The survey asks parents to recall their well-child visit for 2019, which would not be useful data at this time, and could add stress on to

			the providers.
1.06	5/13/2020	Added research study activities may be delivered by Zoom video conferencing.	Due to the 2020 outbreak of Covid-19, we included Zoom video conferencing as a way to implement study activities.
1.07	1/25/22	Increased sample size to 60 patients/provider	Due to the participation of more providers than anticipated (95 vs 80) and because of variation among providers, our statistician has suggested to increase the sample size to 60 patients per provider to allow the power to detect a meaningful difference between the control group and intervention group.

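### The primary model leaves out each provider's baseline coverage and the practice-size stratum, both fixed before randomisation, and so gives up precision in a 20-practice trial

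*Combined protocol and SAP*

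**What the plan says.** Section 9.4.2 defines the primary analysis as a three-level logistic model with one fixed effect, treatment, and random intercepts for practice and provider. Adjustment is then offered as an option: "As secondary analysis, we can add other covariates in the model, e.g., gender, category of practice (urban vs. rural), vaccine rate at baseline". Section 9.4.7 repeats the offer ("we can add other covariates in the model used in the primary analysis"), and so does Section 9.4.9 ("As secondary exploratory analyses, we can add other covariates in the model used in the primary analysis").

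Other sections show what is known before allocation:

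- Section 4.1: "Randomization will occur after baseline assessment".
- Section 8.1, on the chart audit: "To assess variation among providers in the same practice, we will sample records from each participating provider". Baseline is one of its four measurement periods.
- Section 6.3: "We will stratify practices into 2-groups by the number of providers", with a cut at 4 or fewer against 5 or more, and blocks within strata.

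Section 9.2 gives a random-effect variance of 0.75² for providers and 0.01 for practices, and reads the pilot data as showing "very little heterogeneity at the practice level, but significant heterogeneity at the provider level".

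**The concern.** With only 20 practices, a strong baseline predictor is the cheapest source of precision available. The trial collects one: the coverage of each participating provider before randomisation. It sits at the level that dominates the standard error, yet the primary model does not use it. The protocol instead sought power by raising the audit to 60 charts per provider (Section 9.2; version 1.07 in Section 10.4). More charts shrink only the sampling error within a provider; they cannot shrink the differences between providers.

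The stratum is a smaller matter. When randomisation is stratified, the analysis would normally carry the stratum; leaving out a prognostic one makes the standard error too large. Section 9.4 never names it, while its covariate examples include urban against rural, which was not a stratification factor.

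The optional wording also leaves the adjusted analysis undefined: which covariates, in what form, and whether baseline enters per provider or per practice.

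**Working it through.** **Inputs from the documents.** Coverage 0.40 against 0.53; σ_a² = 0.01 (practice); σ_b² = 0.75² = 0.5625 (provider); 10 practices per arm; 4 providers × 30 charts in the power simulation; 95 providers × 60 charts now (Section 9.2). Two-sided 0.05 (Section 9.4.1).

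**Assumptions.** r = 0.3, 0.5 or 0.7. Baseline charts per provider are 20 to 34. This is inferred from the amendment log, where version 1.05 (March 2020) reads "Increased sample size to 160 patients/practice" and the move to 60 per provider came only in January 2022: 160/8 = 20 in the largest practices, 160/4.75 = 34 on average (95/20 = 4.75 providers per practice). For the 4 × 30 design, 20 to 30 baseline charts are used.

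**Formula.** Marginal rates 0.40 and 0.53 correspond to conditional logits −0.457 and 0.135, a difference of 0.592. With J providers per practice and m charts per provider,

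Var = Σ over arms of { f·σ_a²/10 + [f·σ_b² + 1/(m·E[p(1−p)])]/(10·J) },

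where E[p(1−p)] is 0.2135 (control) and 0.2209 (intervention). Unadjusted, f = 1. Adjusted, f = 1 − r²·rel, with rel = 0.5725/(0.5725 + 1/(m_base × 0.2135)): 0.71, 0.79, 0.81 and 0.88 at 20, 30, 34 and 60 baseline charts. Power uses the noncentral t, 18 df.

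**The plan's own figure (4 × 30, unadjusted).** Var = 0.0020 + 0.0281 + 0.0077 = 0.0378; SE 0.194; power 0.82 (0.86 with a normal test). A 1,000-run simulation of the three-level logistic model gave 0.86. The claim of over 0.80 reproduces.

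**95 × 60, unadjusted.** Var = 0.0020 (practice) + 0.0237 (provider) + 0.0032 (charts) = 0.0289; SE 0.170; power 0.91. Providers account for 0.0237/0.0289 = 82%. Unlimited charts would remove only 0.0032, or 11% (SE 0.160).

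**Adjusted for baseline coverage.**

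| r | 95 × 60: SE | Variance cut | Power | 4 × 30: variance cut | Power |
|---|---|---|---|---|---|
| none | 0.170 | – | 0.91 | – | 0.82 |
| 0.3 | 0.165 | 6% | 0.92 | 5–6% | 0.84 |
| 0.5 | 0.154–0.156 | 16–18% | 0.95 | 14–16% | 0.87–0.88 |
| 0.7 | 0.137–0.141 | 31–35% | 0.98 | 28–31% | 0.92–0.93 |

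Example (r = 0.5, 34 baseline charts): f = 1 − 0.25 × 0.806 = 0.798; Var = 0.798 × 0.0257 + 0.0032 = 0.0237. The equivalent number of practices is 20 × 0.0289/0.0237 ≈ 24; at r = 0.3 it is about 21. With 60 baseline charts the cuts would be 7%, just under 20% and 38%.

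**Simulation checks.** 20,000 simulated trials per setting (95 providers in practices of 2–8, 34 baseline charts, least squares on empirical logits) gave cuts of 6%, 17% and 34%, with the mean estimate unchanged at 0.59. The mixed logistic model, simulated for 4 × 30 at r = 0.5, moved the mean SE from 0.196 to 0.180 and power from 0.86 to 0.91. The 95 × 60 design was not simulated with that model.

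**Stratum.** If it explained all of σ_a² = 0.01, the unadjusted SE would be too large by √(0.0289/0.0269) = 1.036, or 1.028 for 4 × 30. The test is then slightly conservative, with size about 0.042.

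**The case against.** The strongest reply is that nothing is broken. One primary model is prespecified, it is valid, and it meets its power target; which model is primary is a legitimate choice. That stands, and it is why this is a recommendation and not an error. But the target is met at a 13-point effect. Section 2.2 reports gains of 5–10% from earlier combined provider strategies. At 0.40 against 0.50 the same formula gives power 0.72 unadjusted, and about 0.74, 0.79–0.80 and 0.86–0.88 adjusted for r of 0.3, 0.5 and 0.7.

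The gain rests on an unknown r. This also stands. The intervention aims to change provider behaviour, pilot results varied within and across practices, and the pandemic began near baseline, so r could be low. At r = 0.3 the gain is small.

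Some providers may have no baseline of their own. Substituting the practice rate recovers little when practice variance is only 0.01, so the figures above are for providers who have a baseline value.

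Freedom to pick a result after seeing the data is limited, because model (1) is fixed as primary. The looseness concerns only how adjusted results are specified and weighed.

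A late change by a team that cannot be blinded has a credibility cost. The date of the amendment, the blinded analyst (Section 6.3) and retention of model (1) reduce that cost but do not abolish it.

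**Conclusion.** The point holds as a loss of efficiency, not as bias or an invalid test. That both variables are missing from model (1) is certain from the text. On the plan's variances, adjustment for baseline coverage cuts the variance in the 95 × 60 design by 6% at r = 0.3, 16–18% at 0.5 and 31–35% at 0.7. At r = 0.5 that exceeds the 11% that unlimited further charts could give. Nearly all the gain comes from baseline coverage; the reason to include the stratum is that the analysis should reflect the randomisation. The size rests on r, on the inferred baseline chart count, and on 0.40 and 0.53 being overall proportions, as Section 9.2 words them. It should be changed, but the trial does not depend on it.

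**What to change.** Before any unblinded outcome analysis, issue a dated amendment to Section 9.4.2:

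- Primary model at 24 months, and the same model at 36: treatment, size stratum (≤4 or ≥5 providers), the provider's baseline coverage of the same outcome, and random intercepts for practice and provider.
- Enter baseline coverage as a proportion, or as an empirical logit with 0.5 added to each cell. The two gave the same results in simulation. The 0.5 keeps 0% and 100% defined: at the lowest initiation rate in Section 2.2 (2%, 2014 data) the chance of no vaccinated child is 0.98^60 = 0.30 with 60 charts and 0.98^20 = 0.67 with 20.
- Use the practice's baseline rate for a provider without one, and report how many this affects.
- Keep model (1) as a sensitivity analysis.
- Remove baseline rate from the optional lists in Sections 9.4.2, 9.4.7 and 9.4.9, except as a moderator.

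The cost is the amendment and two fixed effects. If neither covariate were prognostic, one degree of freedom would cost at most about 0.003 in power; two would take the 4 × 30 design from 0.821 to 0.816. If Year 2 results have already been seen by arm, model (1) should stay primary and the adjusted model be reported as supportive.

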9.4.3 ANALYSIS OF THE SECONDARY ENDPOINT(S)

We will use mediation analysis to test whether the provider's capability and provider's beliefs about their capabilities mediate the intervention's effect on vaccination outcomes.

Define the provider's beliefs about their capabilities by M_{ij} , we can write the model as

$$M_{ij} = \alpha_0 + trt_{ijk}\alpha_1 + c_i + e_{ij} \quad (2)$$

$$\text{logit } P(y_{ijk}=1) = \beta_0 + trt_{ijk}\beta_1 + M_{ij}\gamma + a_i + b_{ij} \quad (3)$$

We are interested in testing the hypothesis $H_0: \alpha_1\gamma = 0$ vs. $H_1: \alpha_1\gamma \neq 0$. The joint significance test⁷⁹ can be used to test the significance of the mediation effect. We include random effect c_i to capture the correlation of the provider's capabilities within the same practice. The indirect effect, i.e., the effect of intervention to the outcome through the mediator is specified as the product of α_1 and γ . The direct effect of treatment on outcome is denoted by β_1 . We can use a similar model for provider's capability.

Finally, we can also include the interaction of treatment and mediator in Model (3), to test whether the mediator is also a moderator of treatment in the "mediator moderator" model.

We will use mediation analysis to test whether the intervention effect on vaccination outcomes is mediated by the degree of practice change as measured by an 18-item HPV vaccine delivery score.

For implementation outcomes (fidelity, acceptability, appropriateness), we will complete a descriptive analysis. Parental satisfaction will be modeled in a three-level (practice, provider, and child's parent) linear mixed effects model. Descriptive statistics will be given on implementation fidelity, the acceptability and appropriateness of the intervention for providers, parental satisfaction with care, and cost. Of note, fidelity score is measured at the practice level every 6 months in the intervention group only. Parental satisfaction is measured in both study groups at baseline and 24 months. Provider acceptance and appropriateness is measured in intervention group at 24 months.

Denote by y_{it} the fidelity score of practice i at time t . Repeated measures of fidelity score will be modeled by mixed effects models.

$$y_{it} = \beta_0 + \beta_1 t + a_i + e_{ij}, \quad (4)$$

Where β_1 is the slope for the temporal change in the fidelity score, a_i is the random intercept for practice i , and e_{ij} is the error term. By testing $\beta_1 = 0$, we can see if there is a significant increase in the fidelity score over time in the intervention group. We can add a random slope of time in this model to capture the heterogeneity in such a temporal change.

As another example, parental satisfaction will be modeled in a three-level (practice, provider, and child's parent) linear mixed effects model:

$$y_{ijk} = \beta_0 + trt_{ijk}\beta_1 + a_i + b_{ij} + e_{ijk}$$

For cost, it is beyond the scope of this project to complete a cost-effectiveness analysis that includes all long-term related social costs and benefits (e.g., prevention of cancer, reducing costs of secondary prevention activities). Rather, we will prospectively assess the cost to replicate the intervention in practice.⁷⁷ To generalize beyond Missouri, geographic wage data from the Bureau of Labor Statistics, and average Medicaid allowable rates will establish a minimum on cost reimbursement

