3 OBJECTIVES AND ENDPOINTS

OBJECTIVES	ENDPOINTS	JUSTIFICATION FOR ENDPOINTS	PUTATIVE MECHANISMS OF ACTION
Primary			
To evaluate the effectiveness of the intervention to improve optimal HPV vaccine use.	The proportion of eligible preteens who initiate the HPV vaccine before their 13th birthday, at 24 months. The proportion of eligible preteens who complete the HPV vaccine before their 13th birthday, at 24 months.	Consistent with CDC Guideline Recommendations	
Secondary			
To assess the sustainability of intervention benefit.	The proportion of eligible preteens who initiate the HPV vaccine before their 13th birthday, at 36 months. The proportion of eligible preteens who complete the HPV vaccine before their 13th birthday, at 36 months.		
Tertiary/Exploratory			
To determine whether the intervention effect on vaccination outcomes is mediated by providers' increased belief in their capabilities to provide on-time HPV vaccination (primary outcome) and by their increased use of a presumptive, announcement approach to recommend HPV vaccine (secondary)	The proportion of eligible preteens who initiate the HPV vaccine before their 13th birthday, at 24 months. The proportion of eligible preteens who complete the HPV vaccine before their 13th birthday, at 24 months.		Mediation

OBJECTIVES	ENDPOINTS	JUSTIFICATION FOR ENDPOINTS	PUTATIVE MECHANISMS OF ACTION

To explore if the intervention effect on vaccination outcomes is mediated by the degree of practice change as measured on an 18-item HPV vaccine delivery score.
 
To inform scalability of the intervention, we will assess implementation fidelity, the acceptability and appropriateness of the intervention for providers, parental satisfaction with care, and cost.
	
The proportion of eligible preteens who initiate the HPV vaccine before their 13th birthday, at 24 months.
 
The proportion of eligible preteens who complete the HPV vaccine before their 13th birthday, at 24 months.
 
Implementation fidelity, the acceptability and appropriateness of the intervention for providers, parental satisfaction with care, and cost.
		Mediation

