9.3 POPULATIONS FOR ANALYSES

Data analyses will adhere to the intention-to-treat principle, allowing 12-months grace period to implement practice changes. The primary analysis will compare the overall proportion of eligible preteens who initiated and completed HPV vaccination in the intervention and control practices at 24 months, using Year 2 measurements for vaccine use. Maintenance of change will be assessed using Year 3 measurements.

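### Section 9.4.3 assigns the mediators no visit and adjusts for no baseline values, so coverage already achieved, or stable provider differences, could be reported as mediation

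*Combined protocol and SAP*

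**What the plan says.** Section 9.4.3 sets up the mediation analysis with "Define the provider's beliefs about their capabilities by M_{ij} , we can write the model as" and then gives model (2) for the mediator and model (3) for vaccination. The mediator M_ij has subscripts for practice and provider only. The plan says a similar model can be used for provider capability. It adds a further mediation analysis, of whether the effect is "mediated by the degree of practice change as measured by an 18-item HPV vaccine delivery score", again without a visit. In the same section the fidelity model is indexed by time ("the fidelity score of practice i at time t"), and parental satisfaction, acceptability and appropriateness are each given visits.

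The outcome is fixed. Section 3 lists, for the mediation objectives, "The proportion of eligible preteens who initiate the HPV vaccine before their 13th birthday, at 24 months", and the same for completion. Section 9.3 makes the comparison "in the intervention and control practices at 24 months, using Year 2 measurements for vaccine use", after a 12-month grace period.

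The mediators have three scheduled values. Section 8.1 states "At baseline and at 12- and 24-months, in addition to the EMR audit described above, all participating providers will complete a brief survey", and for the practice assessment, "HPV vaccination procedures will be reassessed in a similar manner at 12- and 24- months". Section 1.3 agrees.

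Models (2) and (3) contain treatment, the mediator (model 3) and random effects. Section 9.4.2 mentions the baseline vaccination rate of a provider or practice only as an optional covariate in secondary analyses of the primary model.

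**The concern.** A mediator has to come before the outcome it is meant to explain. Of the two post-randomisation values, the 12-month one falls at the start of the Year 2 window and the 24-month one at its end. The plan does not choose, so the choice could be made after the results are known. The label of the outcome (24 months) invites pairing it with the 24-month survey.

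The intervention includes audit and feedback of coverage and help with self-monitoring (Sections 4.1 and 6.1.2). A provider whose figures have improved may report more confidence because of them, and model (3) would credit that association to gamma, the effect of confidence on vaccination. A second route gives the same result: providers who have always vaccinated more may always be more confident. Without baseline values, model (3) cannot separate that stable difference from mediation.

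At stake is Hypothesis 2 in Section 4.1, that the intervention works through capability and confidence. Section 9.2 gives this aim its own significance level and power statement.

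**Working it through.** **Timeline.** Reading Year 2 as months 12 to 24 (Sections 8.1 and 9.3):

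| Time | Mediator measure | Vaccination data |
|---|---|---|
| Baseline | survey, delivery score | baseline 12-month records |
| Months 0–12 | – | Year 1 (grace period) |
| Month 12 | survey, delivery score | – |
| Months 12–24 | – | Year 2 records = mediation outcome |
| Month 24 | survey, delivery score | – |

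Section 5.1 samples children aged 10–13 with a visit in the period, and the outcome counts any dose before the 13th birthday. Some counted doses therefore predate Year 2, so even the 12-month survey does not precede every dose.

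**The plan's own figure.** Section 9.2 (Aim 2) claims sufficient power at 0.025 for a difference of 0.14 from 0.4, and 0.13 from 0.5 or 0.6. Simulating its design (20 practices × 4 providers × 30 children, practice variance 0.01, provider variance 0.75²), with the rates read as marginal proportions, gives power 0.886, 0.822 and 0.866, which agrees. Read as rates at random effect zero, they give 0.758, 0.694 and 0.762. None of these depends on when M is measured, so they do not bear on this point.

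**False mediation, first simulation.** Inputs from the plan: 95 providers in 20 practices, 60 children each, provider SD 0.75, practice SD 0.1, level 0.025. Assumed: M = 0.6·trt + r·z + noise, where z is the provider's standardised vaccination effect, and M has no effect on vaccination. The provider's empirical logit is regressed on arm and M (2,000 replicates).

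| r | gamma = 0 rejected | joint test rejected |
|---|---|---|
| 0 | 2.7% | 1.9% |
| 0.2 | 34% | 24% |
| 0.3 | 72% | 52% |
| 0.4 | 95% | 72% |

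Because z is a provider effect shared by M and the outcome, nothing in this set-up is specific to month 24.

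**Separating timing from stable differences.** Same design at r = 0.3, letting provider effects correlate from year to year (assumed values). Rejection of gamma = 0:

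| Year-to-year correlation | 24-month M | 12-month M | 12-month M + baseline M + baseline rate |
|---|---|---|---|
| 1.0 | about 68–69% | 69% | 5% |
| 0.8 | about 68–69% | 46% | 14% |
| 0.6 | about 68–69% | 26% | 13% |

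Moving to month 12 helps only as far as providers change between years. The baseline adjustment gives a large further reduction.

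**Second simulation.** Here M responds to the provider's own observed rate (80 providers, 60 children each, marginal rates 0.40 and 0.53, 300 runs per setting). Joint test rejections at r = 0.3 and 0.5:

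- Treatment shifts M directly by 0.5 SD: 42% and 83% for a 24-month M; 31% and 63% for a 12-month M fed by Year 1 rates.
- Shift of 0.8 SD: 60% and 99%; 48% and 92%.
- No direct shift, 24-month M: 6% and 19%.
- No feedback (r = 0): 2% or less throughout.

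**The case against.** The strongest reply is that nothing in the documents says the 24-month survey will be used. That is correct. A reader might infer from the outcome's label that the plan pairs it with the 24-month mediator, but the defect is an open choice that allows this pairing.

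A reader might also take the 34%, 72% and 95% as the cost of measuring at month 24. They are not. They come from a provider effect shared by mediator and outcome, and a 12-month mediator gives nearly the same figures when providers are stable. It follows that moving to month 12 alone is no cure.

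The feedback path should not be overstated either. The item in Table 3 on providers reviewing their own figures concerns baseline data, and baseline rates go to both arms (Section 6.1.1); later monitoring is mainly a QI-team activity. Because feedback starts in the first month, 12-month confidence is exposed to it too. For the delivery score, a practice-level measure obtained with the practice manager, no feedback path was simulated.

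Restricting the outcome to children undosed at month 12 looks like a clean way to order events. As a main analysis it would condition on a status the intervention may already have changed, and counting only first doses would drop completion. Finally, Year 1 is the declared grace period, so a 12-month mediator may be immature. That is a real cost of choosing it.

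What stands is that no visit is named, no baseline value enters models (2) and (3), and all the data needed to correct both are scheduled.

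**Conclusion.** The point holds as a gap in specification with a cheap remedy. As written, Section 9.4.3 lets a significant joint test arise from coverage already achieved or from stable provider differences, and the analysis could not distinguish either from mediation. The size depends on correlations, treatment shifts in M and year-to-year stability that the documents do not give. Over the ranges assumed, false mediation by the joint test runs from about 2% with no association to 99% under the strongest assumptions. The percentages show that inflation can be large; they do not estimate what this trial will produce.

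Residual provider-level confounding remains even after the fix (5% to 14% against a nominal 2.5%), so mediation should be reported as supportive of the mechanism and not as proof of it. Mediation is a secondary objective in Section 1.1 and tertiary/exploratory in Section 3. The comparison in Section 9.4.2 is untouched.

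**What to change.** In Section 9.4.3:

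- Define the primary mediator as the 12-month provider survey (belief and announcement approach) and, for practice change, the 12-month delivery score.
- Pair it with Year 2 initiation and completion in the full Year 2 sample.
- Add the baseline mediator value to models (2) and (3), and the baseline provider or practice vaccination rate to model (3). For provider belief: M_ij,12 = α0 + trt·α1 + M_ij,0·α2 + c_i + e_ij, and logit P(y_ijk = 1) = β0 + trt·β1 + M_ij,12·γ + M_ij,0·δ1 + R_ij,0·δ2 + a_i + b_ij, where R_ij,0 is the baseline rate.
- Use the 24-month mediator only as a sensitivity analysis. If an analysis of children undosed at the 12-month survey is wanted, label it a sensitivity analysis and state its post-randomisation selection.
- State that mediation results are supportive evidence on mechanism.

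The cost is wording. Surveys, delivery assessments and baseline records are already collected, and keeping the full sample leaves the sample basis of the Aim 2 power statement as it is. Mediator change that arises only in Year 2 will be missed by the primary mediation analysis, and a rule is needed for providers without baseline values.
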